## Determination of Subjects for Analysis

All subjects that completed 4 weeks of elevated night pacing. Subjects that were unable to tolerate or withdrew from the treatment during the first 4 weeks because of safety or other issues will not be included in this efficacy analysis.

## **Device-measured activity levels – 8 weeks**

### Hypothesis

There is an improvement in daytime activity levels over an additional 4 week period of elevated night pacing after an initial 4 week period of elevated night pacing compared to that period of 4 weeks with the elevated night pacing programmed OFF after the initial 4 weeks period of elevated night pacing.

### Analysis Methods

Activity levels over time will be characterized over time from the 4 week visit to the 8 week visit and compared between the subjects with the elevated pacing programmed ON versus OFF. Analysis will be similar to the 4 week activity level endpoint. The date of the 8 week visit and the 3 days prior to and subsequent to it will comprise the 8 week window.

Those periods will be retrieved from the Cardiac Compass activity level data using SAS code similar to the following

```
DATA Activity_Week8;
  SET Activity_Consent;

  /*      Straddle the week 4 date - the 4 week date and the 3 days
  before and after the 4 week date */
  IF (w4date-3) LE entryday-consdt LE (w4date+3) THEN DO;
    period=1;
    OUTPUT;
  END;

  /*      Straddle the week 8 date - the 8 week date and the 3 days
  before and after the 8 week date */
  IF (w8date-3) LE entryday-consdt LE (w8date+3) THEN DO;
    period=2;
    OUTPUT;
  END;

RUN;
```

The analysis will be performed using linear mixed effects modeling, using SAS code similar to

```
PROC MIXED DATA=Activity_Week8;
  CLASS pt period trt;
  MODEL activityperday = period trt period*trt;
  RANDOM pt;
  LSMEANS period trt period*trt / PDIFF=all ALPHA=0.05;
RUN;
```

A significant p-value for the interaction between period and treatment would suggest that there is incremental value in continuing high rate pacing from week 4 to week 8.

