	
 
• Symptom Assessment
 
• Heart Rate
 
 
4 Week In-Clinic Follow Up Visit (Randomization):
 
 
• Medications
 
• Physical Assessment (including weight, heart rate and blood pressure)
 
• NYHA classification
 
• MN Living with Heart Failure Questionnaire
 
• 6 Minute Walk Test
 
• Blood Draw
 
• Echo
 
• Device Interrogation (initial)
 
• Save-to-Media (initial)
 
• Program the sleep function to OFF if randomization assignment is OFF (and program the pacing parameters)
 
• Device Interrogation (final) - this needs to be completed at the end of the visit after programming has been completed
 
• Save-to-Media (final)
 
• Adverse Events (report new/assess ongoing AEs), Study Deviations, System Modifications, Device Deficiencies, Crossovers (as they occur)
 
 
6 Week Telephone Call Follow Up Visit:
 
 
• Symptom Assessment
 
• Heart Rate
 
 
8 Week In-Clinic Follow Up Visit:
 
 
• Medications
 
• Physical Assessment (including weight, heart rate and blood pressure)
 
• NYHA classification
 
• MN Living with Heart Failure Questionnaire
 
• EQ-5D-5L Questionnaire
 
• 6 Minute Walk Test
 
• Blood Draw
 
• Echo
 
• Device Interrogation (initial)
 
• Save-to-Media (initial)
 
• Program the sleep function to OFF if subject still has sleep function ON (and program the pacing parameters)
 
• Device Interrogation (final) - this needs to be completed at the end of the visit after programming has been completed
 
• Save-to-Media (final)
 

--	--

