Pacing at an elevated rate for 100% of the day may accelerate changes in cardiac structure, but could be symptomatic if elevated rates sustained for long periods of time. Elevating heart rate for 5 hours during sleep at night may reduce the sensation to elevated rates and minimize symptoms for the patients. However, a heart rate dose of 5 hours will increase the overall duration required to promote dilation in the LV chamber. A measurable change in LV volumes was measured at 2 weeks of 100% pacing at 125bpm in animals [7], so a reasonable therapy duration of 100bpm for 5 hours per day would be 4 to 8 weeks of pacing before changes in LV volume would be measured. Measurement of biomarkers including matrix metalloproteinases (MMPs) and tissue inhibitors of metalloproteinases (TIMPs) may be useful in understanding the time course of changes that lead changes in geometry. The matrix metalloproteinases (MMPs) are part of an enzymatic system that contribute to the remodeling of the extracellular matrix during rapid pacing-induced cardiomyopathy [14]. MMP-1, MMP-2, and MMP-3 were shown to increase in abundance at 7 days following initiation of rapid pacing, and were temporally related to a measured decrease in the collagen content as well as a lengthening of cardiomyocytes. TIMPs are also involved in inhibiting MMPs enzymatic activity and elevated TIMP-1 with reduction in MMPs were reported in HFpEF patients with LV hypertrophy [15].

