**Figure 2: Sleep Function On During the Day**

The Sleep Function will be programmed to deliver the Sleep Rate between 5a.m. and 11:30pm, using a Bed Time of 5a.m. and a Wake Time of 11:30pm.

The Sleep Function was designed to operate in conjunction with Rate Responsive pacing; however, the Rate Profile Optimization feature that automatically optimizes was not developed with 5 hours of 100bpm imposed on patients. Therefore, Rate Profile Optimization will be turned OFF while the Sleep Function is programmed ON.

The Sleep Function is suspended following any parameter programming operations. If the Sleep Function is suspended, the pacing rate will immediately return to the programmed Lower Rate (100bpm per this protocol) until the next Bed Time is reached. At the initial programming visit of this protocol, subjects will be evaluated for whether they are symptomatic at a Lower Rate of 100bpm. Subjects will leave the Baseline visit experiencing a Lower pacing rate of 100 bpm until 5am the next morning, when Bed Time for the Sleep Function is reached. After the elevated pacing has been turned ON, any telemetry activation, such as programming, magnet application or CareLink transmission will suspend the Sleep Function and the pacemaker will immediately return to the Lower Rate of 100 bpm until 5am.

If a pacemaker reaches Estimated Replacement Indicator (ERI), the device will automatically turn OFF the Sleep Function and reprogram the pacemaker to VVI 65 mode.

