#### **10.5. Schedule of Events**

Clinical data is collected at designated time points throughout the study as indicated in Table 4 below. Data will be collected using eCRFs, an electronic data management system for clinical studies. See Section 16.2. Data Management for more information. At the baseline, 4 week, 8 week, and 12 week visits subjects are to fill out the MN Living with Heart Failure Questionnaire and perform a 6 Minute Walk Test. At the same visits, an echocardiogram must be done, for which instructions are provided in an Echocardiography Handbook (provided under separate cover). A blood draw must also be done,

(instructions are provided under separate cover.) The device programming should occur after all other study procedures are complete, except for the final device interrogation and save-to-media. The EQ-5D-5L Questionnaire will only be collected at the Baseline and 8 week visits.

In addition to eCRF data, non-eCRF data will be collected to include device interrogation files/save-to-media and digital echo data.

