### 10.12.1. Programming Recommendations

Table 8 lists the programming recommendations applicable to study subjects who still have elevated night pacing ON. (All subjects should have elevated night pacing OFF by the end of the 8 week visit.)

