### 10.14. **12 Week Visit (Study Exit)**

At the completion of the 12 week follow-up visit, subjects will be exited from the study since this is the final visit. The 12 week follow-up visit and exit visit should be combined, and both a 12 week follow-up eCRF and a Study Exit eCRF need to be completed. The following procedures must be performed / data are required to be collected at the 12 week visit:

- Medications
- Physical Assessment (including weight, heart rate, symptoms and blood pressure)
- NYHA Class
- MN Living with Heart Failure Questionnaire
- 6 Minute Walk Test
- Echo\*
- Blood Draw\*\*
- Device Interrogation (initial)
- Save to Media (initial)
- Program the sleep function and pacing parameters to elevated night pacing OFF (see Table 8) for subjects who still have their pacemaker programmed to elevated night pacing ON.

- Device Interrogation (final) - this needs to be completed at the end of the visit after programming has been completed
- Save-to-Media (final)
- Adverse Events (report new/assess ongoing AEs), Study Deviations, System Modifications, Device Deficiencies

\* The echo must be sent to the Echo Core Laboratory for analysis, with a copy of the echo remaining at the site. Details of the Echo Core Laboratory, type of echo to be performed, and the review process will be provided in an Echocardiography Handbook (provided under separate cover).

\*\* The blood sample must be sent to the Blood Core Laboratory for analysis. Details of the blood core lab and the blood draw process will be provided under separate cover.

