## Analysis Methods

Activity levels over time will be characterized over time from baseline to the 4 week visit. Daily activity level is recorded by the Cardiac Compass feature in most devices. Since subjects enrolled in the study have had their pacemaker for at least 6 month, they will have activity levels prior to enrollment in the study. The daily activity levels in the 2 weeks prior to the date of therapy initiation (period 1) will be compared to daily activity levels around the 4 week visit. Specifically, the activity level on the date of the 4 week visit and the 3 days prior to and subsequent to that date will comprise the week 4 comparison group (period 2). Those periods will be retrieved from the Cardiac Compass activity level data using SAS code similar to the following, where the Activity\_Baseline data set contains all of the Cardiac Compass dates (entryday), along with the date of therapy initiation (therapydt) on each record.

```
DATA Activity_Week4;
  SET Activity_Baseline;
  IF -8 < entryday-therapydt < 0 THEN DO;
    period = 1;
    OUTPUT;
  END;
  IF -15 < entryday- therapydt LE -8 THEN DO;
    period=1;
    OUTPUT;
  END;
  /*      Straddle the week 4 date - the 4 week date and the 3 days
before and after the 4 week date */
  IF (w4date-3) LE entryday- therapydt LE (w4date+3) THEN DO;
    period=2;
    OUTPUT;
  END;
RUN;
```

The analysis will be performed using linear mixed effects modeling, using SAS code similar to

```
PROC MIXED DATA=Activity_Week;
  CLASS pt period;
  MODEL activityperday = period;
  RANDOM pt;
  LSMEANS period / PDIFF=all alpha=0.05;
RUN;
```

Additional analyses, using similar methodology, may be done to explore other potential effects of therapy, including whether there is an immediate impact on activity following therapy initiation.

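### Device-measured activity: the visit-centred 7-day windows include days after pacing is switched off, and the random-intercept model treats a subject's days as independent replicates

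*SAP*

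**What the plan says.** SAP 7.9.5 compares daily device-recorded activity between periods. For the 4-week endpoint the later period is "the activity level on the date of the 4 week visit and the 3 days prior to and subsequent to that date", set against the 14 days before therapy. For the 8-week endpoint the week-4 window is the first period, and the second is defined by "The date of the 8 week visit and the 3 days prior to and subsequent to it will comprise the 8 week window". The code matches the prose.

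Both windows straddle a programming change. At week 4 the Protocol Synopsis says "Program the sleep function to OFF if randomization assignment is OFF". At week 8, Protocol 10.12.1 says "All subjects should have elevated night pacing OFF by the end of the 8 week visit". Protocol 10.5 puts programming last in the visit: "The device programming should occur after all other study procedures are complete". Protocol 10.14 makes provision at week 12 "for subjects who still have their pacemaker programmed to elevated night pacing ON", so full compliance at week 8 is not taken for granted.

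Both analyses use PROC MIXED on the daily records with `RANDOM pt` as the only random effect. There is no subject-by-period term and no REPEATED statement. The 8-week test is the period-by-treatment interaction. The SAP reads a significant result as a sign that continuing pacing adds value, and SAP 4.2 carries nominally significant effects forward to week 12.

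**The concern.** There are two separate faults.

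**Window.** The 8-week hypothesis compares four more weeks of pacing with four weeks without it. Days after switch-off in the ON arm are not part of that pacing. In the OFF arm, days after switch-off do not belong in the starting level. The first lowers the ON arm's end value and the second lowers the OFF arm's start value, so both pull the contrast towards zero.

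**Model.** With a subject intercept only, the seven (or 14) daily values in a period act as independent replicates of the period effect. If subjects differ in how much they truly change, or if neighbouring days are alike, the standard error is too small and the test rejects too often.

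The faults do not offset each other. With no true effect there is nothing to dilute, so any excess of false positives stands. At stake is one ancillary signal in a study that is not powered for any endpoint.

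**Working it through.** **Inputs.** Window definitions, code and model: SAP 7.9.5. Switch-off times: Protocol Synopsis, 10.5 and 10.12.1. Allocation 2:1: SAP 5.1. Up to 30 subjects: SAP 6, taken here as 20 ON and 10 OFF with no dropout. The documents give no SD, day-to-day correlation, effect size or fade rate for activity. There is therefore no planned figure to reproduce, and everything below rests on assumed values.

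**1. Day count.** The visit day is counted as on therapy because programming comes last.

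| Arm | Week-4 window | Week-8 window |
|---|---|---|
| ON | 7 on | 4 on, 3 off |
| OFF | 4 on, 3 off | 7 off |

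**2. Share of the effect kept.** The contrast is C = (ON8 − ON4) − (OFF8 − OFF4). Let the effect be 1 while paced and r(d) = 2^(−d/h) at d days after switch-off, with visits at days 28 and 56.

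- SAP window: w = (4 + r(1) + r(2) + r(3))/7 and C = 2w − 1 − f, where f is the OFF arm's mean residual effect over days 25 to 31 after switch-off.
- Seven days ending the day before the visit: C = 1 − f′, with f′ averaged over days 21 to 27.

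Instant loss: w = 4/7, so C = 8/7 − 1 = 1/7 = 14%, against 100%.

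Half-life 7 days: r = 0.906, 0.820, 0.743; w = 6.469/7 = 0.924; f = 0.064; C = 1.848 − 1 − 0.064 = 0.784. With the pre-visit week, f′ = 0.095 and C = 0.905.

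| Half-life | Full effect while on: SAP v pre-visit | Effect growing linearly to day 56: SAP v pre-visit |
|---|---|---|
| 28 days | 46% v 45% | 69% v 65% |
| 14 days | 67% v 69% | 78% v 78% |
| 7 days | 78% v 91% | 82% v 88% |
| 3 days | 69% v 100% | 74% v 93% |
| 1 day | 39% v 100% | 51% v 93% |
| Instant loss | 14% v 100% | 33% v 93% |

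The last column is a share of the day-56 effect. Its 93% ceiling is the mean of days 49 to 55, 52/56.

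The 4-week endpoint is less exposed, because only the 10 OFF subjects are affected. With full effect while on, instant loss keeps (20 + 10 × 4/7)/30 = 86% and a 7-day half-life keeps (20 + 9.24)/30 = 97%.

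**3. Standard error of the interaction.** Set the daily SD to 1 and let τ be the between-subject SD of true change.

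- True variance: (τ² + 2/7)(1/20 + 1/10).
- Model: pooled residual on 30×2×6 + 28 = 388 df, with expected mean square [360 + 28 × 3.5 × (τ² + 2/7)]/388.

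At τ = 0.5 the true variance is 0.5357 × 0.15 = 0.0804, SE 0.283. The mean square is (360 + 52.5)/388 = 1.063, so the model SE is √(1.063 × 0.2857 × 0.15) = 0.213, a ratio of 0.75. The critical value 1.966 then acts like 1.966 × 0.75 = 1.48, a two-sided error of about 14%.

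Simulated type I error (8,000 runs per setting, 20 v 10 subjects, 7+7 days, nominal 5%):

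| Setting | `RANDOM pt` model |
|---|---|
| Change SD 0 / 0.25 / 0.5 of daily SD | 5% / 8% / 14% |
| AR(1) 0.1 / 0.3 / −0.2 | 7% / 14% / 1.6% |
| Stable weekday pattern (SD 0.5) alone | 3% |
| Weekday pattern with change SD 0.25 / 0.5 | 4% / 10% |
| Weekday pattern with AR(1) 0.3 | 10% |

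A t-test on one mean change per subject gives 4.5% to 5.2% in all of these. With 12 v 6 subjects (not every device records activity) the model gives 13% at change SD 0.5 and 14% at AR(1) 0.3. The 4-week period test (30 subjects, 14+7 days) gives 17% at change SD 0.5, 15% at AR(1) 0.3 and 1.9% at AR(1) −0.2; the subject-level test gives 5% in each.

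**The case against.** The window loss needs a fast fade that the Protocol does not describe. Protocol 5.1 reasons that it "would be 4 to 8 weeks of pacing before changes in LV volume would be measured", and Protocol 7.2 leaves the time course of reversal to be observed. At a 14-day half-life the pre-visit week gains at most 2 points, and at 28 days it loses 1 to 4. This stands. A fast fade of activity is not excluded, since activity need not follow LV volume, but the window is a cheap improvement rather than a demonstrated error.

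The size of the model fault is also unknown. Negative autocorrelation or a stable weekly pattern makes the test conservative. The endpoint is ancillary, no multiplicity adjustment is planned, and the SAP says only that code will be similar to that shown. This limits the weight but not the logic: no other covariance structure is described. For the same week-8 comparison, the SAP's t-tests of walk distance, questionnaires, blood markers and continuous echo measures already use one change per subject.

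Three objections bear on the remedy.

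- A pooled t-test misbehaves if the arms differ in change SD. With SD 0.5 in the OFF arm only it rejects about 8% of the time, and with SD 0.5 in the ON arm only about 3%. Welch's version stays near 5%. The planned model gives 11.6% and 7.8%.
- Subjects who leave before week 8 need a stated window.
- The telemetry reason for dropping the visit day applies to subjects who stay ON at week 4, not to those programmed OFF that day. Ending the window on the visit day would be a smaller change.

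**Conclusion.** The concern holds. The SAP's prose and code put 3 off-therapy days out of 7 into the OFF arm's week-4 value and the ON arm's week-8 value when programming follows the Protocol. The cost is material only if the effect fades within about a week, and negligible at half-lives of 14 days or more.

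The model is the stronger point. As specified it is valid only if subjects hardly differ in true change and days are close to independent. Under moderate departures the nominal 5% test runs at about 8% to 14%, and under some structures it falls below 5%. Fade shapes, SD ratios, correlations and the 20 v 10 split are all assumptions.

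Confidence is high in the logic and lower in the size. This should be fixed, but it does not touch the 4-week safety and tolerability endpoint that is to guide the decision to go on.

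**What to change.** - **Window.** For weeks 4 and 8, use the seven days ending the day before the visit. Leave out the visit day: while the Sleep Function is ON, telemetry "will suspend the Sleep Function and the pacemaker will immediately return to the Lower Rate of 100 bpm until 5am" (Protocol 8.4), so it is not a usual day for subjects who stay ON.
- **Date selection.** Select by calendar visit date in both programs. At present both use `w4date`, but one counts from therapy start and the other from consent, and Protocol Table 5 allows up to 30 days between enrolment and baseline.
- **Test.** Take one mean per subject per period. For week 4 to week 8, compare mean changes ON v OFF with Welch's two-sample t-test. For the 4-week endpoint, use a paired t-test of the 14 pre-therapy days against the pre-visit week.
- **Acceptable alternative.** Keep the mixed model, add a subject-by-period random effect and use between-subject degrees of freedom. Simulated error is 3.3%, 4.1% and 4.8% at change SD 0, 0.25 and 0.5 with 28 df.
- **Early leavers.** Keep the SAP's rule of using activity up to exit, and say which seven days that means.
- **Carry-over.** State that any effect persisting in the OFF arm at week 8 stays in the contrast whichever window is used.

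The cost is SAP text and code only, as the daily data are already retrieved. Intervals will usually be wider, and the new window gains nothing if the effect fades slowly.

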#### Analysis Methods

A paired comparison of the measurement at the 8 week visit compared to the measurement at the 4 week visit period compared to the value at the start of the period will be calculated. A two-sided paired t-test will be performed testing the hypothesis

$$H_0: \mu_{ON} = \mu_{OFF}$$

$$H_a: \mu_{ON} \neq \mu_{OFF}$$

Where  $\mu_{ON}$  = difference in NT-proBNP, troponin or LVEF from week 4 to week 8 for subjects in the ON arm and  $\mu_{OFF}$  = difference in those measurements in subjects in the OFF arm

SAS code similar to the following will be used to evaluate the 8 week ancillary safety endpoints, where the variables in the VAR statement will equal the difference between the 8 week and 4 week measurements:

```
PROC TTEST;
  CLASS trt;
  VAR ntpobnppdiff;
RUN;

PROC TTEST;
  CLASS trt;
  VAR troponindiff;
RUN;

PROC TTEST;
  CLASS trt;
  VAR lvefdiff;
RUN;
```

An ANCOVA model may also be used for all analyses prospectively planned as T-tests, in addition to the T-tests for this and other similar ancillary objectives comparing the 4 and 8 week data by randomized treatment group. ANCOVA models may be implemented using SAS code similar to

```
PROC GLM;
  CLASS trt;
  MODEL ntpobnppdiff= trt ntpobnpp0;
  LSMEANS trt / pdiff cl alpha=0.05;;
RUN;
```

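### The randomised 8 week activity test is an unadjusted change-score contrast whose standard error is too small; a subject-level ANCOVA on data already extracted would mend both

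*SAP*

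**What the plan says.** - **8 week model.** SAP 7.9.5 (Device-measured activity levels – 8 weeks) stacks daily activity from two windows, each a visit date plus and minus 3 days. It fits "MODEL activityperday = period trt period*trt" with `RANDOM pt` as the only random term, followed by "LSMEANS period trt period*trt / PDIFF=all ALPHA=0.05". The reading is fixed in advance: "A significant p-value for the interaction between period and treatment would suggest that there is incremental value in continuing high rate pacing".
- **Week-4 window.** The condition "IF (w4date-3) LE entryday-consdt LE (w4date+3) THEN DO" takes in up to 3 days after the randomisation visit.
- **Pre-therapy data.** The 4 week activity analysis in the same section pulls two blocks before therapy starts, by "IF -8 < entryday-therapydt < 0 THEN DO" and "IF -15 < entryday- therapydt LE -8 THEN DO". Neither block enters the 8 week data step or model.
- **Adjustment.** SAP 7.9.2 (8 weeks) says: "An ANCOVA model may also be used for all analyses prospectively planned as T-tests". Activity is planned as a mixed model, so it falls outside that wording.
- **Size.** SAP 5.1 aims for 30 subjects on night pacing, randomised 2:1. No SD, correlation, effect size or power is given for activity.

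**The concern.** The protocol (section 14) treats the ON v OFF comparison from week 4 to week 8 as the evidence for a real therapeutic effect, because the first 4 weeks are single-arm and unblinded. SAP 4.2 and 7.9.8 then use nominal significance to choose what is followed up at week 12. Two features of the activity model bear on that.

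First, a change score fixes the weight on week-4 activity at 1 and uses nothing earlier, although each subject has a multi-day pre-therapy record. In a very small trial that can waste information, and it leaves the estimate exposed to chance imbalance at week 4.

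Second, a random intercept alone assumes that a subject's level is the same in both windows apart from independent daily noise. If subjects drift between week 4 and week 8 for reasons unrelated to treatment, the daily rows overstate the information and the p-value is too small. The second feature has the larger consequence.

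**Working it through.** The plan states no figure for this test, so there is none to reproduce.

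**Inputs from the documents.** 30 subjects at 2:1 gives 20 ON and 10 OFF if nobody is lost; the documents do not state this split. Each window has 7 days. The two pre-therapy conditions select days −7 to −1 and −14 to −8, which is 14 days.

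**Assumptions.** Correlation ρ between windows of 0.5 to 0.9. Daily SD of 0.5 to 1.0 times the between-subject SD. Two patterns: equal correlation among the three windows, or correlation that decays with time (AR(1)).

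**Step 1: what is estimated.** With balanced data the interaction equals (week 8 − week 4 mean in ON) − (the same in OFF). A fitted random-intercept model and the direct calculation both gave 0.1533 on one simulated data set.

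**Step 2: the standard error.** Take between-subject variance 1, daily variance s², k = 7 days, and ρ as the correlation of a subject's underlying levels in the two windows.
- True variance of a subject's change: 2(1−ρ) + 2s²/7.
- Rows: 30 × 2 × 7 = 420. Error df in the SAP model: 420 − 30 − 2 = 388, against 28 for one change per subject.
- Expected residual variance in the SAP model: [30 × 2 × 6 × s² + 28 × (7(1−ρ) + s²)] / 388. The model uses 2/7 of this as the variance of a change.
- At ρ = 0.7 and s = 1: true 0.6 + 0.286 = 0.886. Residual (360 + 28 × 3.1)/388 = 1.152, so the model uses 0.329. SE ratio √(0.329/0.886) = 0.61. Nominal 1.97 SE becomes 1.20 true SE, which is about 77% coverage. Simulated type I error was 23%.
- At ρ = 0.5 and s = 0.5: true 1.071. Residual (90 + 28 × 3.75)/388 = 0.503, model variance 0.144, SE ratio 0.37, coverage about 53%.
- At ρ = 0.9 and s = 1, simulated type I error was 11% to 13%, so coverage was 87% to 89%.

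**Step 3: precision against a correctly computed change score.** Here ρ is the correlation of window means with unit variance. The variance factors are:
- change score: 2(1−ρ);
- ANCOVA on week 4: 1−ρ²;
- ANCOVA on week 4 and pre-therapy: 1 − 2ρ²/(1+ρ) under equal correlation, and 1−ρ² under AR(1).

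For q covariates at N = 30, multiply by 27/(27−q). For two covariates this is 27/25 = 1.08.

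| ρ | Equal correlation, both covariates | × 1.08 | AR(1), both covariates | × 1.08 |
|---|---|---|---|---|
| 0.5 | 0.67 | 0.72 | 0.75 | 0.81 |
| 0.7 | 0.71 | 0.76 | 0.85 | 0.92 |
| 0.9 | 0.74 | 0.80 | 0.95 | 1.03 |

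Entries are ratios to the change-score variance. Simulation with daily noise, 20 v 10 subjects and only the three pre-visit week-4 days as covariate gave ratios of about 0.70 to 0.81 under equal correlation and 0.78 to 1.10 under AR(1). The ANCOVA interval covered about 95% and was 1.2 to 2.5 times as wide as the one from the SAP code.

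**Step 4: chance imbalance.** Given a week-4 difference d between arms, the change score errs by −(1−ρ)d. One standard error of d is √(1/20 + 1/10) = 0.39 SD. The miss is then 0.5 × 0.39 = 0.19, 0.3 × 0.39 = 0.12 or 0.1 × 0.39 = 0.04 SD at ρ = 0.5, 0.7 or 0.9.

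**The case against.** The strongest reply is that this is an ancillary endpoint in an unpowered feasibility study (SAP 6) without multiplicity control (SAP 7.5). SAP 7.2 allows further exploratory analyses, and week 4 to week 8 change between arms is the contrast used for the other continuous endpoints too. That stands as to severity. It does not excuse the standard error: those other endpoints compare one change per subject, whereas activity counts daily rows.

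Three stronger readings are tempting, and the documents do not support them.

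- *Adjustment will narrow the interval that the SAP code gives.* It will not. That interval is too narrow to begin with, and the corrected one is wider. The gain in Step 3 is against a valid change-score analysis.
- *The change score is biased.* Over repeated randomisations it is unbiased. The miss in Step 4 applies only once a particular imbalance has occurred.
- *The gain comes from the unused pre-therapy days.* Only in part. Under AR(1) the large-sample variance is 1−ρ² with or without them, so the gain comes from freeing the week-4 slope. Adding pre-therapy activity to the change score alone gains nothing under equal correlation, and about 4% to 7% under AR(1) before the lost degree of freedom.

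It is also fair that 20 v 10 is an upper limit. SAP 7.9.5 says only most devices record activity, and subjects must complete 4 weeks. With 18 subjects the factor for two covariates would be 15/13 = 1.15, not 1.08, so a modest gain could disappear.

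**Conclusion.** The point holds in two parts. The 8 week activity estimate is an unadjusted change-score contrast that leaves out pre-therapy data already extracted and lies outside the optional ANCOVA. Its standard error is too small whenever subjects' levels shift between windows: coverage is about 53% to 89% over the assumed range. The second part matters more, because the SAP reads this p-value directly.

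The efficiency gain is real but conditional: roughly 20% to 30% less variance under equal correlation, and about 20% down to none under decaying correlation, with a loss of up to 10% in the least favourable setting at ρ = 0.9. These sizes rest on correlations and daily SDs that the documents do not give, and on no attrition. Nothing confirmatory is invalidated. The change should be made because a nominally significant interaction is taken as evidence for continued pacing and steers the week 12 tests.

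**What to change.** In SAP 7.9.5 (8 weeks), before unblinding:

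1. Make the main estimate a subject-level ANCOVA: mean daily activity in the week-8 window = arm + mean of the week-4 days before the visit + mean of the 14 pre-therapy days. Report the adjusted ON minus OFF difference with its 95% CI.
2. Use only pre-visit week-4 days as covariate, so that no post-randomisation day enters it.
3. If the period-by-treatment model stays as a sensitivity analysis, add a subject-by-period random effect or reduce the data to one mean per subject per period.
4. State how a subject who exits before a full week-8 window contributes, since the SAP uses activity up to exit.
5. Use one date origin when merging the data steps: the 4 week code counts days from therapy start, the 8 week code from consent.

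The cost is two degrees of freedom (26 instead of 28 at 30 subjects) and a few lines of text and code. No new data are needed. Readers should be told that the interval will be wider than the present code would give, and why.
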